Table ITSE.1.	Objectives and Endpoints.....	21
Table ITSE.2.	Treatment Regimens.....	32
Table ITSE.3.	Target Glucose Values for Adjustment of Insulin Therapy	33
Table ITSE.4.	Basal Insulin Hypoglycemia Assessment	35
Table ITSE.5.	Summary of Basal Insulin Adjustments after Hypoglycemia Assessment.....	35
Table ITSE.6.	Prandial Insulin Doses and Corresponding Self Monitored Blood Glucose Values Pattern Adjustment Plan	37
Table ITSE.7.	LY900014 or Insulin Lispro Adjustment Algorithm Pattern Adjustment Plan	37
Table ITSE.8.	Concomitant Medications	40
Table ITSE.9.	Insulin to Carbohydrate Ratio for the MMTT Prandial Insulin Dose	48

List of Figures

Figure

Page

Figure ITSE.1. Illustration of study design for Clinical Protocol I8B-FH-ITSE.....24

List of Appendices

Appendix		Page
Appendix 1.	Abbreviations and Definitions.....	67
Appendix 2.	Clinical Laboratory Tests.....	71
Appendix 3.	Study Governance Considerations.....	72
Appendix 4.	Hepatic Monitoring Tests for Treatment-Emergent Abnormality.....	76
Appendix 5.	World Health Organization Classification for Diabetes.....	77
Appendix 6.	New York Heart Association Cardiac Disease Classification	78
Appendix 7.	Classification of Contraceptive Methods.....	79

1. Synopsis

Title of Study:

A Prospective, Randomized, Double-Blind Comparison of LY900014 to Insulin Lispro, Both in Combination with Insulin Glargine or Insulin Degludec in Adults with Type 2 Diabetes

Rationale:

A prandial insulin with faster-onset and/or faster-offset characteristics might reduce glycemic excursions and the incidence of delayed postprandial hypoglycemia compared to currently available rapid-acting insulin analogs. Rapid-acting insulins, such as Humalog®, have been shown to have a more rapid onset of action compared to human insulin; however, the general consensus is that they are not rapid enough to match carbohydrate absorption, whether delivered by pump or syringe/pen injector, limiting efficacy. An ultra-rapid-acting prandial insulin that shifts the pharmacokinetic (PK) and glucodynamic profiles of insulin to provide an even faster onset of action, would better match carbohydrate absorption and allow for efficacious dosing immediately prior to meals or even after meals. Ultra-rapid insulin (URI) could be useful in the treatment of type 1 diabetes (T1D) and type 2 diabetes (T2D) in adults and children when delivered by multiple daily injections (MDI) or by continuous subcutaneous insulin infusion (CSII).

The aim of this study is to demonstrate that an ultra-rapid formulation of insulin lispro, LY900014, is non-inferior to insulin lispro on glycemic control as measured by change from baseline to Week 26 in hemoglobin A1c (HbA1c) in patients with T2D when administered in a double-blind manner as prandial insulin in combination with basal insulin glargine or degludec in accordance with local regulations.

Objectives/Endpoints:

Objectives	Endpoints
Primary Objective	

 To test the hypothesis that LY900014 is non-inferior to insulin lispro on glycemic control (non-inferiority margin [NIM]=0.4% for HbA1c) in patients with T2D, when administered as prandial insulin (0 to 2 minutes prior to the meal), in combination with basal insulin glargine or insulin degludec for 26 weeks 	
 Difference between LY900014 and insulin lispro in change from baseline to Week 26 in HbA1c
Multiplicity Adjusted Objectives	

 To test the hypothesis that LY900014 is superior to insulin lispro in controlling 1-hour postprandial glucose (PPG) excursions, when administered as prandial insulin 	
 Difference between LY900014 and insulin lispro in the 1-hour PPG excursion (serum glucose measured 1 hour after the start of the meal minus fasting serum glucose) from a mixed-meal tolerance test (MMTT) at Week 26

 To test the hypothesis that LY900014 is superior to insulin lispro in controlling 2-hour PPG excursions when administered as prandial insulin 	
 Difference between LY900014 and insulin lispro in the 2-hour PPG excursion (serum glucose measured 2 hours after the start of the meal minus fasting serum glucose) from an MMTT at Week 26

Objectives	Endpoints

 To test the hypothesis that LY900014 is superior to insulin lispro on improving glycemic control (HbA1c) when administered as prandial insulin 	
 Difference between LY900014 and insulin lispro in change from baseline to Week 26 in HbA1c
Other Secondary Objectives	

 To compare LY900014 and insulin lispro with respect to the rate of severe hypoglycemic events 	
 Rate (events/patient/100 years) of severe hypoglycemic events from baseline through Week 26

 To compare LY900014 and insulin lispro with respect to the incidence and rate of documented symptomatic postmeal hypoglycemia 	
 Rate (events/patient/year and/or events/patient/30 days) and incidence (percent of patients with at least 1 event) of documented symptomatic postmeal hypoglycemia within 1 and 2 hours after start of a meal from baseline through Week 26

 To compare LY900014 and insulin lispro with respect to the incidence and rate of documented symptomatic hypoglycemia 	
 Rate (events/patient/year and/or events/patient/30 days) and incidence (percent of patients with at least 1 event) of documented symptomatic hypoglycemic events from baseline through Week 26

 To compare LY900014 and insulin lispro with respect to 1,5-Anhydroglucitol (1,5-AG) 	
 Change from baseline in 1,5-AG values at Week 26

 To compare LY900014 and insulin lispro with respect to 10-point self-monitored blood glucose (SMBG) profiles 	
 Change from baseline in 10-point SMBG values at week 26

 To compare LY900014 and insulin lispro with respect to total, basal, and prandial insulin dose 	
 Change from baseline in total, basal and prandial insulin doses and prandial/total insulin dose ratio at Week 26

 To compare LY900014 and insulin lispro with respect to the proportion of patients achieving HbA1c targets 	
 The proportion of patients with HbA1c <7% and ≤6.5% at Week 26

Summary of Study Design:

Study I8B-FH-ITSE is a Phase 3, prospective, randomized, double-blind, multinational, multicenter, 2-group, parallel, active-controlled study conducted in patients with T2D currently treated with basal insulin in combination with at least 1 prandial insulin injection OR premixed insulin with at least 2 injections daily.

Treatment Groups and Duration:

Patients will be randomized to 1 of the 2 treatment groups in 2:1 ratio (LY900014:insulin lispro). The 2 treatment groups, LY900014 and insulin lispro, will be administered immediately (0-2 minutes) prior to each meal in a double-blind manner. The study includes a 1-week screening period and an 8-week lead-in period, followed by a 26-week treatment period and a 4-week safety follow-up period.

Number of Patients:

Approximately 705 patients will be screened to achieve 564 randomized patients and 480 patients completing 26 weeks of treatment. Approximately 450 Chinese patients will be randomized. The other 114 randomized patients are planned to be from other countries, which may include Mexico, Argentina, Brazil, India and Ukraine. The final participating countries and allocated patient numbers will be adjusted based on the actual condition.

Statistical Analysis:

The primary analysis is for the treatment period through Week 26.

Efficacy analyses will be conducted on all randomized patients using an intention-to-treat (ITT) approach according to the treatment the patients are assigned. The analyses for the primary and multiplicity adjusted objectives will include data collected prior to permanent discontinuation of investigational product (IP). When change from baseline is included as a response variable of analysis models, the patient will be included in the analysis only if a baseline and at least 1 post-baseline measurement are available. Selected efficacy analyses will also be conducted using the Per Protocol (PP) and Completer populations.

Safety analyses will be conducted on the Safety population. Analyses of AEs will include 2 sets of analyses, unless otherwise specified. The first set of analyses will include data collected prior to permanent discontinuation of IP. The second set of analyses will include all data collected during the course of the entire study including the follow-up visit, regardless of IP use. Analyses of hypoglycemia will use data collected prior to permanent discontinuation of IP, while analyses for post-treatment may be performed as needed. Analyses of safety laboratory measurements will be performed on all data during the planned treatment period regardless of IP use.

Baseline is defined as the last nonmissing measurement at or before the randomization visit (Visit 8), unless otherwise specified.

The primary efficacy comparison will be based on the contrast between LY900014 and insulin lispro at Week 26 (Visit 18) from the mixed-effect model repeated measure (MMRM) analysis of change from baseline in HbA1c, including data collected from all randomized patients prior to permanent discontinuation of IP through Week 26. If the upper limit of the 2-sided 95% confidence interval (CI) for the least squares (LS) mean difference in the change from baseline in HbA1c for LY900014 minus insulin lispro is below +0.4%, LY900014 will be declared non-inferior to insulin lispro. The model for this analysis will include the fixed class effects of treatment, strata (country, type of basal insulin, and number of prandial doses at entry), visit, and treatment-by-visit interaction, as well as the continuous, fixed covariate of baseline value.

A graphical approach (Bretz et al. 2011) for multiple comparisons will be used to strongly control the overall Type I error (2-sided alpha level of 0.05) for testing the treatment effect for the primary and the following multiplicity adjusted objectives: superiority of LY900014 compared with insulin lispro for 1-hour PPG excursion at Week 26, 2-hour PPG excursion at Week 26, and change from baseline to Week 26 in HbA1c.

An analysis of covariance (ANCOVA) model with strata (country, type of basal insulin, baseline HbA1c [$\leq 8.5\%$, $>8.5\%$], and number of prandial doses at entry), and treatment as fixed effects and baseline as a covariate will be used to analyze the 1-hour and 2-hour PPG excursions. However, if the percentage of the patients with missing MMTT data at baseline is higher than 15%, a constrained longitudinal data analysis model (Liu et al. 2009; Lu 2010) will be used instead. Analyses details will be documented in the statistical analysis plan (SAP).

Hypoglycemia rates will be summarized for periods of 30 days, 1 year, and 100 years (severe hypoglycemia only). The rate of severe hypoglycemia per 100 years will be compared between treatment groups using the empirical

method. For each of the other categories of hypoglycemia, the number of hypoglycemia events during a specific period (rate) after randomization (for example, 0 to 12 weeks of treatment period) will be analyzed by using a negative binomial regression model. The model will include treatment and the baseline hypoglycemia rate (measured during lead-in) as a covariate. An offset defined as the log transformation of treatment exposure in the specific period (days)/365.25 days (or 30 days) will be included in the model to estimate the rate of hypoglycemia per year (or per 30 days). The proportion of patients with at least 1 hypoglycemic event in each category (incidence) during a specific period after randomization will be analyzed using a logistic regression model including treatment and baseline hypoglycemia rate value in the model.

Continuous safety variables, as well as the change from baseline for these variables, will be analyzed by MMRM or ANCOVA models. For categorical variables, Fisher's exact test will be used to compare treatment groups unless otherwise specified.

Change from baseline to last-observation-carried forward endpoints for the European Quality of Life – 5 Dimensions 5 Level (EQ-5D-5L), Insulin Treatment Satisfaction Questionnaire (ITSQ), and Work Productivity and Activity Impairment Questionnaire General Health (WPAI-GH) will be analyzed using ANCOVA models.

References:

- Lu K. On efficiency of constrained longitudinal data analysis versus longitudinal analysis of covariance. *Biometrics.* 2010;66(3):891-896.

2. Schedule of Activities

Study Procedure	Study Screening	Lead-In Period						Intensive Titration Period								Maintenance Period			Safety Follow-Up	ED
		8	9a	10	11	12a	13	14a	15	16	17	18	Treatment Period							
eCRF Visit Number	1	2	3a	4a	5	6a	7	8	9a	10	11	12a	13	14a	15	16	17	18	801	ED ^b
Visit Window (± days)		3	3	3	3	3	3	4	3	3	7	7	7	7	7	7	7	7	7	
Time on Study Relative to First Active Treatment Dose (weeks)	-9	-8	-7	-6	-4	-2	-1	0	1	2	4	6	8	10	12	18	22	26	30	
Informed consent signed	X																			
IWRS	X	X	X	X	X	X	X	X	X	X	X	X	X	X	X	X	X	X	X	X
Patient eligibility review	X																			
Randomization ^c								X												
Clinical Assessments																				
Patient demographics	X																			
Medical history and preexisting conditions	X																			
Physical exam/height ^d	X																			
Concomitant medication	X	X	X	X	X	X	X	X	X	X	X	X	X	X	X	X	X	X	X	X
AEs and product complaints	X	X	X	X	X	X	X	X	X	X	X	X	X	X	X	X	X	X	X	X
Body weight ^e	X	X			X		X	X		X	X		X		X	X	X	X	X	X
Vital signs: blood pressure/pulse rate ^f	X	X			X		X	X		X	X		X		X	X	X	X	X	X
ECG (12-lead local)	X																			
Diabetes and nutrition counseling ^g		X																		
Transfer to insulin lispro ^h		X																		
Transfer to allowed study basal insulin regimen ⁱ		X																		
Basal and prandial insulin dose assessment ^j		X	X	X	X	X	X	X	X	X	X	X	X	X	X	X	X	X		
Titrate basal insulin ^j		X	X	X	X	X	X													
Titrate prandial doses (as needed) ^k								X	X	X	X	X	X	X						

Study Procedure	Study Screening	Lead-In Period						Intensive Titration Period								Maintenance Period			Safety Follow-Up	ED
		2	3a	4a	5	6a	7	Treatment Period								16	17	18		
eCRF Visit Number	1	2	3a	4a	5	6a	7	8	9a	10	11	12a	13	14a	15	16	17	18	801	ED ^b
Visit Window (± days)		3	3	3	3	3	3	4	3	3	7	7	7	7	7	7	7	7	7	
Time on Study Relative to First Active Treatment Dose (weeks)	-9	-8	-7	-6	-4	-2	-1	0	1	2	4	6	8	10	12	18	22	26	30	
Ancillary Supplies/Diaries/IP																				
Dispense blood glucose meter, monitoring and ancillary supplies and complete training ^{l,m}		X						X		X	X		X		X	X	X	X		
Distribute study diary		X			X		X	X		X	X		X		X	X	X	X		
Diary use training ^m		X																		
Collect study diary and transfer diary data to eCRF (InForm) ⁿ					X		X	X		X	X		X		X	X	X	X	X	X
Train on collecting 4-point and 10-point SMBG Profile ⁿ		X																		
Review 4-point SMBG profiles ^o			X	X	X	X	X	X	X	X	X	X	X	X	X	X	X	X	X	X
Remind patient of 10-point SMBG requirements ^p						X	X							X			X			
Review 10-point SMBG profiles								X							X			X		X ^q
Review/discuss hypo data			X	X	X	X	X	X	X	X	X	X	X	X	X	X	X	X		X
Dispense IP		X			X			X			X		X		X	X	X			
Patient returns used and unused study drug supplies					X			X			X		X		X	X	X	X		X
Drug accountability					X			X			X		X		X	X	X	X		X

Study Procedure	Study Screening	Lead-In Period						Intensive Titration Period								Maintenance Period			Safety Follow-Up	ED
		2	3a	4a	5	6a	7	Treatment Period								16	17	18		
eCRF Visit Number	1	2	3a	4a	5	6a	7	8	9a	10	11	12a	13	14a	15	16	17	18	801	ED ^b
Visit Window (± days)		3	3	3	3	3	3	4	3	3	7	7	7	7	7	7	7	7	7	
Time on Study Relative to First Active Treatment Dose (weeks)	-9	-8	-7	-6	-4	-2	-1	0	1	2	4	6	8	10	12	18	22	26	30	
Laboratory Assessments																				
Patient fasts prior to visit		X						X											X	X
MMTT ^f								X											X	
Urinalysis panel	X																			
Pregnancy test ^s	X							X												
Follicle-stimulating hormone test ^t	X																			
Chemistry	X							X											X	X
Fasting serum glucose		X																		
Hematology	X							X											X	X
1,5-Anhydroglucitol								X			X				X				X	X
Hemoglobin A1c	X						X	X			X		X		X				X	X
Lipid profile								X											X	X
Anti-insulin lispro antibodies		X						X		X	X				X				X	X
Health outcomes questionnaires^u																				
ITSQ		X						X											X	X
EQ-5D-5L		X						X											X	X
WPAI-GH		X						X											X	X

Abbreviations: AE = adverse event; BP = blood pressure; ECG = electrocardiogram; eCRF = electronic case report form; ED = early discontinuation; EQ-5D-5L = European Quality of Life – 5 Dimensions 5 Level; FBG = fasting blood glucose; hypo = hypoglycemia; IP = investigational product; ITSQ = Insulin Treatment Satisfaction Questionnaire; IWRS = interactive web response system; MMTT = mixed-meal tolerance test; SMBG = self-monitored blood glucose; WPAI-GH = Work Productivity and Activity Impairment Questionnaire General Health.

- a Telephone visits are indicated by shaded columns. Activities include:
 - Record visit in IWRS.
 - Collect AEs and concomitant medications.
 - Review blood glucose readings and study drug doses. Recommendations for basal or prandial insulin adjustments are provided, if necessary by the investigator or designee.
 - Review hypoglycemic events.
 - Provide reminders regarding scheduled visits, fasting, and SMBG profiles, as applicable.
- b Patients who have been randomized will be asked to return for the ED visit in a fasting state unless patient is already fasting and at the site when the decision to discontinue is made. Patients who discontinue during the lead-in period prior to randomization, and who are not already at the site, will be asked to return for the ED in a nonfasting state and all activities should be completed except for laboratory tests and completing the questionnaires (ITSQ, EQ-5D-5L, and WPAI-GH).
- c Randomization should occur after all Visit 8 procedures including MMTT. If MMTT is rescheduled post Visit 8, randomization should not occur until baseline MMTT is completed. The patient will administer their first dose of study insulin with the first meal after the MMTT has been completed and randomization has occurred.
- d Physical examination shall be performed at Visit 1. It shall be performed at other visits if deemed necessary by the investigator.
- e Patients should be advised to remove their shoes and empty their pockets before the body weight is obtained.
- f Vital sign measurements must be taken before obtaining an ECG tracing and before collection of blood samples for laboratory testing. These measurements should be determined after patients have been seated quietly for at least 5 minutes in a chair with feet on the floor. The arm used for BP measurement should be supported at heart level
- g Initial training at Visit 2 will include diabetes education and nutrition counseling. Appropriate site personnel will administer training and education using locally approved diabetes education/training materials and programs or by using other materials that may be provided by the Sponsor. Patients may be provided abbreviated training and education at visits following Visit 2 based upon patient needs.
- h Only applies to patients treated with insulin glulisine, insulin aspart, regular human insulin, or premixed insulin.
- i Patients will be transferred to insulin glargine U-100 once daily or to degludec U-100 once daily at Visit 2 if the patient enters the study on any other basal insulin regimen. Investigators will determine the appropriate basal insulin regimen for each patient. Basal insulin should be titrated during the 8-week lead-in period to the target FBG. Basal insulin dose may be adjusted if needed to facilitate optimal prandial insulin dosing during the intensive titration period (Weeks 0 to 12) or for safety reasons. Thereafter, during the maintenance period (Weeks 12 to 26), it is expected that adjustments to basal insulin doses would be for safety reasons such as hypoglycemia or unacceptable hyperglycemia.
- j Assessments of the basal insulin dose should be made at minimum weekly during the lead-in period, including Weeks -5 and -3. Assessment of the prandial insulin dose should be made at minimum weekly during the initial 12 weeks after randomization, including Weeks 3, 5, 7, 9, and 11. See also Sections [7.2.1.3](#) and [7.2.1.4](#).

- k During the initial 12 weeks after randomization, the prandial insulin dose (either fixed insulin dose or insulin to carbohydrate ratio) and correction factor (as applicable) should be adjusted as necessary in order to meet the target SMBG levels. During the maintenance period (Weeks 12 to 26), it is expected that prandial insulin dose adjustments would be to maintain glycemic control or for safety reasons such as hypoglycemia or unacceptable hyperglycemia.
- l Glucose monitoring supplies will be dispensed at other visits, as needed.
- m Training may be repeated at other visits, as needed.
- n Study sites will retain study diaries.
- o Patients should be encouraged to measure a minimum of 4 SMBG readings daily to satisfy dose titration. 4-point SMBG is required on three nonconsecutive days in the one week before each visit.
- p Patients should be instructed to perform three 10-point SMBG profiles during a 2-week period. The 10-point SMBG profile is completed over a 1-day period, preferably on 3 nonconsecutive days (weekdays and weekends). Ten-point SMBG profiles should not be performed on the day of MMTT.
- q Review of 10-point SMBG profiles at ED visit will take place only for patients randomized into the study.
- r MMTT can occur 0 to 4 days prior to the visit and patient must be fasting. Time 0 of the MMTT will be when the patient starts to consume the meal. Serial venous blood samples to measure serum glucose will be taken at time -15, 0, 15, 30, 60, 120, 180, and 240 minutes after the start of the meal.
- s Serum pregnancy test that is analyzed by central laboratory must be performed in women of childbearing potential at Visit 1 followed by a local urine or serum pregnancy test within 24 hours prior to IP exposure at randomization (Visit 8) and at other times at the investigator's discretion. When required per local regulations and/or institutional guidelines, local pregnancy testing will occur at mandatory times during the study treatment period, and the local pregnancy test must be kept at site.
- t Follicle-stimulating hormone test must be performed at Visit 1 for a postmenopausal woman who is between 50 and 54 years of age (inclusive) with an intact uterus, not on hormone therapy, and who has had at least 6 months of spontaneous amenorrhea.
- u Health outcomes questionnaires will be administered at the study sites based on the availability of appropriate translations. The questionnaires should be administered prior to other study procedures except at Visit 8 and Visit 18 when questionnaires may be administered following the start of the MMTT.

3. Introduction

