7.2. Method of Treatment Assignment

Patients who meet all criteria for enrollment will be randomized to double-blind treatment at Visit 8. Assignment to treatment groups will be determined by a computer-generated random sequence using an interactive web-response system (IWRS). Patients will be randomized to 1 of the 2 treatment groups in 2:1 ratio (double-blind LY900014 administered at meal time:double-blind insulin lispro administered at meal time). Stratification will be by country (China vs. Other), HbA1c stratum ($\leq 8.5\%$ vs. $> 8.5\%$ at Visit 7), and type of basal insulin during the lead-in period (glargine U-100 vs. degludec U-100), and number of prandial doses at study entry (< 3 vs. ≥ 3).

The IWRS will be used to assign all IP during the study, including insulin lispro during the lead-in period. The IWRS will be used to assign prefilled pens containing double-blind IP to each patient randomized to the 2 blinded study groups. Site personnel will confirm that they have located the correct prefilled pens by entering a confirmation number found on the prefilled pen into the IWRS.

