Hypoglycemia rates will be summarized for periods of 30 days, 1 year, and 100 years (severe hypoglycemia only). The rate of severe hypoglycemia per 100 years will be compared between treatment groups using the empirical method (details will be described in the SAP). For each of other categories of hypoglycemia, the number of hypoglycemia events during a specific period (rate) after randomization (for example, 0-12 weeks of treatment period) will be analyzed by using a negative binomial regression model. The model will include treatment and the baseline hypoglycemia rate (measured during lead-in) as a covariate. An offset defined as the log transformation of treatment exposure in the specific period (days)/365.25 days (or 30 days) will be included in the model to estimate the rate of hypoglycemia per year (or per 30 days). The proportion of patients with at least 1 hypoglycemic event in each category (incidence) during a specific period after randomization will be analyzed using a logistic regression model including treatment and baseline hypoglycemia rate value in the model.

Continuous safety variables, as well as the change from baseline for these variables, will be analyzed either by MMRM or ANCOVA models. For categorical variables, Fisher's exact test will be used to compare treatment groups unless otherwise specified.

The analyses for assessing immunogenicity data will be described in the SAP.

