### 3. Revision History

Statistical analysis Plan (SAP) Version 1 was approved prior to the first patient visit. Version 1 was based on the Protocol I8B-FH-ITSE (ITSE) approved on 27 June 2018.

The main changes of SAP Version 2 are listed below.

- Analysis period of from randomization to Week 26 (including all data regardless of IP use) was added for some of the safety analysis.
- Removed the baseline rate covariate from all hypoglycemia models as there were many critical outliers leading to inaccurate in the LSM and the biases were inconsistent.
- For adjustments of covariates, HbA1c stratum at Visit 7 is changed to HbA1c stratum at baseline to be consistent with the global study ITRN..
- COVID-19 related analyses are added.
- Weights of the graphical testing scheme for the multiple testing of this study are updated by simulation and team decision.

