## 6.2. Adjustments for Covariates

Stratification factors of this study include country (China vs. Other), HbA1c stratum at baseline ( $\leq 8.5\%$  vs.  $>8.5\%$ ), type of basal insulin during the lead-in period (glargine U-100 vs. degludec U-100), and number of prandial doses at study entry ( $<3$  vs.  $\geq 3$ ).

For the primary analysis of HbA1c, the stratification factor of HbA1c stratum (baseline) will not be included. Instead, the continuous value of baseline (Visit 8) HbA1c will be included in the analysis models.

Other efficacy analyses and safety analysis will include the stratification factors as noted in Sections [6.11](#) and [6.12](#).

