**Table 6.5. Summary of Analyses for Endpoints Related to Hypoglycemia**

Endpoint	Analysis Period	Statistical Method
Rate of hypoglycemic events (per patient per 30 days / year) 
 
All Documenteda
 
Nocturnala
 
Documented Symptomatica
 
Non-Nocturnal (Documented and occurred between waking and bedtime)a
 
	0-12, 0-26, 12-26 weeks	Negative binomial regression with treatment and log (exposure/30 days) or log (exposure/365.25 days) as the offset in the model.
Incidence of hypoglycemic events 
 
All Documenteda
 
Nocturnala
 
Documented Symptomatica
 
Non-Nocturnal ( Documented and occurred between waking and bedtime)a
 
	0-12, 0-26, 12-26 weeks	Logistic regression with treatment as an independent variable.
Rate of postmeal hypoglycemic events (per patient per 30 days / year) for all 3 main meals 
 
Documented Symptomatica
 
	$\leq 0.5$ , $\leq 1$ , $\leq 2$ , $\leq 4$ , $>1$ to $\leq 2$ and $>2$ to $\leq 4$ hours after start of a meal within 0-12,12-26, 0-26 weeks	Negative binomial regression with treatment and log (exposure/30 days) or log (exposure/365.25 days) as the offset in the model.
Incidence of postmeal hypoglycemic events for all 3 main meals 
 
Documented Symptomatica
 
	$\leq 0.5$ , $\leq 1$ , $\leq 2$ , $\leq 4$ , $>1$ to $\leq 2$ and $>2$ to $\leq 4$ hours after start of a meal within 0-12,12-26, 0-26 weeks	Logistic regression with treatment as an independent variable.

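### The hypoglycemia rate models omit all four randomization factors, so the rate-ratio interval may be slightly wider than it needs to be

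*Protocol*

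**What the plan says.** Protocol 7.2 sets four randomization factors: "Stratification will be by country (China vs. Other), HbA1c stratum", type of basal insulin during the lead-in, and number of prandial doses at entry. SAP 5.3 repeats them.

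For hypoglycemia other than severe, Protocol 10.3.4 (and the Synopsis) plans a negative binomial rate model: "The model will include treatment and the baseline hypoglycemia rate (measured during lead-in) as a covariate". Incidence "will be analyzed using a logistic regression model including treatment and baseline hypoglycemia rate value in the model". No randomization factor appears in either.

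SAP Version 2 changed this. Its Revision History states: "Removed the baseline rate covariate from all hypoglycemia models as there were many critical outliers". The operative models in SAP Table 6.5 are therefore:
- rate: "Negative binomial regression with treatment and log (exposure/30 days) or log (exposure/365.25 days) as the offset in the model"
- incidence: "Logistic regression with treatment as an independent variable"

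SAP 6.2 sets the general rule: "Other efficacy analyses and safety analysis will include the stratification factors as noted" in Sections 6.11 and 6.12. The hypoglycemia section notes none. The severe hypoglycemia rate is compared by the empirical method, not by a regression with covariates.

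**The concern.** Documented symptomatic hypoglycemia, overall and postmeal, is a named secondary objective, and lower postprandial hypoglycemia is part of the rationale for a faster insulin (Protocol 3.1 and 3.2). The trial randomizes within strata but leaves those strata out of the rate comparison. Any difference in event rate between strata then stays in the unexplained variation, which widens the interval for the rate ratio.

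The SAP does not give a reason for the omission. The four factors are in the models for PPG excursions (6.11.2), 1,5-AG, SMBG and insulin doses (6.11.5), ITSQ (6.11.6) and lead-in insulin doses (6.10). The Version 2 reason for dropping the lead-in rate was extreme covariate values. That reason cannot apply to two-level factors. SAP 6.13.2 already puts HbA1c stratum and basal insulin type into these same models as subgroup factors, so the terms can be fitted.

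**Working it through.** **What the documents allow.** The only design figure is for HbA1c, and it reproduces:
- SE = 1.1 × √(1/320 + 1/160) = 0.1065. Then 0.4/0.1065 − 1.96 = 1.80, which gives 96.4% power against the stated 96%.
- 480/0.85 = 564.7, against the stated 564.

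No rate, dispersion or precision is given for hypoglycemia, so every hypoglycemia input below is an assumption.

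**Baseline check without stratum effects.** 564 patients at 2:1 gives 376 and 188. With mean μ events per patient and dispersion k,

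SE(log rate ratio) ≈ √[(1/376 + 1/188)(1/μ + k)].

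For μ = 3, k = 2: √(0.00798 × 2.333) = 0.1364. Simulated fits gave 0.1366 with treatment only and 0.1370 with the four factors. If the factors are not prognostic, nothing is gained and almost nothing is lost.

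**With stratum effects.** I use three sets of simulated trials with N = 564, 2:1 within strata and mean 3 events. Each trial was fitted with treatment only and with treatment plus the four factors. Set A: 2,500 trials per scenario, 15% early stoppers, true rate ratio 0.75. Set B: 300 trials, k = 2; the SEs shown are from the runs with no treatment effect. Set C: 400 trials, true rate ratio 0.75.

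| Rate change per factor | Fall in SE from adding the factors |
|---|---|
| 1.25-fold | B: 0.1380 to 0.1369, 0.8% |
| 1.3-fold | A: 2.0% (k = 1), 1.1% (k = 2) |
| 1.5-fold | A: 4.5%, 2.7%; B: 0.1417 to 0.1376, 2.9%; C: 3-5% |
| 2, 2, 1.5, 1.5-fold | A: 8.0%, 5.1%; C: 6-9% |
| 2-fold on all four | B: 0.1494 to 0.1381, 7.6% |

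These are mean model-based SEs, which set the interval width. Adding the between-stratum variance to the dispersion by moments would predict more (SE 8.1% larger without the factors at 1.5-fold, k = 2). The fitted models do not show that, so I use the fitted figures.

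**In practical terms, set B:**
- At 1.5-fold and an observed ratio of 1, exp(±1.96 × 0.1417) gives 0.76 to 1.32, and exp(±1.96 × 0.1376) gives 0.76 to 1.31. Since (0.1417/0.1376)² = 1.06, the gain equals about 34 extra patients (0.06 × 564).
- At 2-fold on all four, the interval goes from 0.75-1.34 to 0.76-1.31.

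**Power for the rate ratio:**
- Set C, true ratio 0.75, 1.5-fold: 74.0% to 77.5% (k = 1) and 56.2% to 57.8% (k = 2).
- Set C with 2, 2, 1.5, 1.5-fold: 70.8% to 78.7% and 47.2% to 53.7%. Set A for the same scenario: 69% to 75% and 48% to 52%.
- Set B, true ratio 0.7, 1.25-fold: 71.0% and 70.7%, no difference beyond noise.

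**Sparse windows.** At an assumed mean of 0.3 events and k from 2 to 4, the SE falls by 0.2-0.7% (1.3-fold) and 1.0-1.4% (1.5-fold), with no power change beyond noise.

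**Validity.** With no treatment effect, the treatment-only rate model rejected in 3.3% to 5.3% of set B trials. The adjusted model rejected in 4.5-5.5% of set C trials, and its coverage in set A was 0.943-0.954.

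**Incidence model.** Here adjustment moves the SE of the log odds ratio the other way. In set B it rises from 0.1845 to 0.1857 (1.25-fold), 0.1843 to 0.1866 (1.5-fold) and 0.1838 to 0.1891 (2-fold), about 0.7%, 1.2% and 2.9%. Power rises only slightly (24% to 26% at 2-fold), because the conditional odds ratio lies further from 1.

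**The case against.** Four points limit the concern.

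1. **The loss depends on something the documents do not state.** A reader might infer that the hypoglycemia comparisons are less precise as a matter of fact. That follows only if the factors predict hypoglycemia, and the largest figures need several strong effects at once. This objection stands, so the claim must be conditional.

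2. **It does not extend to incidence.** A reader might infer that the logistic models lose precision too. They do not: adjustment raises the SE of the log odds ratio and changes the target to a conditional odds ratio. This stands, and the incidence models drop out of the point.

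3. **There is no contradiction in the SAP.** It is tempting to read SAP 6.2 as promising adjustment that Table 6.5 fails to deliver. But 6.2 includes the factors only where later sections note them. Other models also lack strata: the HbA1c responder analyses (6.11.5), laboratory tests (6.12.5), vital signs and weight (6.12.6) and antibodies (6.12.7.1). Treatment-only hypoglycemia models fit that safety convention. This stands, so the case rests on precision and not on inconsistency.

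4. **Nothing invalid results.** The endpoints are outside the alpha-controlled family (SAP 6.5), no power is claimed for them, and type I error is not inflated. This lowers the importance. It does not remove the gain available for the rate ratio, since the factors are already recorded and adjustment costs almost nothing when they turn out not to matter.

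**Conclusion.** The omission is confirmed: the non-severe hypoglycemia rate models contain none of the four randomization factors and, since Version 2, no baseline covariate at all. The consequence is a possible and modest loss of precision in the rate ratio. Under the stated assumptions, the avoidable part of the SE is about 1-2% at 1.25- to 1.3-fold per factor, 3-5% at 1.5-fold and 5-9% with 2-fold effects. It is smaller in sparse postmeal windows and nil if the factors are not prognostic. The point does not cover the logistic incidence models or severe hypoglycemia, and it does not question the removal of the lead-in rate. It is a cheap improvement to secondary comparisons, not a flaw in their validity.

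**What to change.** In SAP Table 6.5, for documented symptomatic hypoglycemia and the other non-severe, non-sparse categories:

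- Add country (China vs Other), HbA1c stratum, type of basal insulin and number of prandial doses as fixed effects to the negative binomial models, and take the rate ratio from that model.
- Name the HbA1c term as the baseline stratum of SAP 6.2, as in the other SAP models. Randomization used the Visit 7 value, so a patient's stratum can differ between the two.
- Report group rates by averaging predictions over the observed strata. About 80% of patients (450/564) are planned from China, so equally weighted LS means would describe a different population.
- Use the treatment-only model where the total event count falls below a minimum fixed in the SAP before unblinding. Table 6.5 has six postmeal windows in three periods, and without a fixed threshold the choice of model would depend on the data.

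Leave the logistic incidence models and the severe hypoglycemia analyses as they are. A stratum-adjusted logistic model could be added only as a sensitivity analysis.

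The cost is SAP wording and a few model terms, with no new data. The one drawback is the extra rule for sparse windows.
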